14.3.1.2 Unsolicited Adverse Events

Figure 34: Participant-Level Incidence of Non-Serious Unsolicited Adverse Events in the 28 Days Post Dosing by MedDRA® System Organ Class and Maximum Severity – Participants 9-17 Years Old – Safety Population

Similar Figures:

Figure 35: Participant-Level Incidence of Non-Serious Unsolicited Adverse Events in the 28 Days Post Dose 1 by MedDRA® System Organ Class and Maximum Severity – Participants 2-8 Years Old – Safety Population

Implementation Note: This will be similar to Figure 34. Groups include: 2-8 yrs, 10^9 TCID₅₀ Sing2016 M2SR, 1 or 2 Doses; 2-8 yrs, 10^8 TCID₅₀ Sing2016 M2SR, 1 Dose; 2-8 yrs, Placebo, 1 or 2 Doses

Figure 36: Participant-Level Incidence of Non-Serious Unsolicited Adverse Events in the 28 Days Post Dose 1 by MedDRA® System Organ Class and Maximum Severity – All Participants – Safety Population

Implementation Note: This will be similar to Figure 34. Groups include: Vaccine Recipients, Placebo Recipients

Figure 37: Participant-Level Incidence of Non-Serious Unsolicited Adverse Events in the 28 Days Post Dose 2 by MedDRA® System Organ Class and Maximum Severity – Participants 2-8 Years Old – Safety Population

Implementation Note: This will be similar to Figure 34. Groups include: 2-8 yrs, 10^9 TCID₅₀ Sing2016 M2SR, 2 Doses; 2-8 yrs, Placebo, 2 Doses

Figure 38: Participant-Level Incidence of Non-Serious Unsolicited Adverse Events in the 28 Days Post Any Dose by MedDRA® System Organ Class and Maximum Severity – Participants 2-8 Years Old – Safety Population

Implementation Note This will be similar to Figure 34. Groups include: 2-8 yrs, 10^9 TCID₅₀ Sing2016 M2SR, 2 Doses; 2-8 yrs, Placebo, 2 Doses

Figure 39: Participant-Level Incidence of Adverse Events of Special Interest by MedDRA® System Organ Class and Maximum Severity – Participants 9-17 Years Old – Safety Population

Implementation Note: This will be similar to Figure 34. Groups include: 9-17 yrs, 10^9 TCID₅₀ Sing2016 M2SR, 1 Dose; 9-17 yrs, Placebo, 1 Dose

Figure 40: Participant-Level Incidence of Adverse Events of Special Interest by MedDRA® System Organ Class and Maximum Severity – Participants 2-8 Years Old – Safety Population

Implementation Note: This will be similar to Figure 34. Groups include: 2-8 yrs, 10^8 TCID₅₀ Sing2016 M2SR, 1 Dose; 2-8 yrs, 10^9 TCID₅₀ Sing2016 M2SR, 1 Dose; 10^9 TCID₅₀ Sing2016 M2SR, 2 Doses; 2-8 yrs, Placebo, 1 or 2 Doses

Figure 41: Participant-Level Incidence of Adverse Events of Special Interest by MedDRA® System Organ Class and Maximum Severity – All Participants – Safety Population

Implementation Note: This will be similar to Figure 34. Groups include: Vaccine Recipients, Placebo Recipients

Figure 42: Participant-Level Incidence of Serious Adverse Events by MedDRA® System Organ Class and Maximum Severity – Participants 9-17 Years Old – Safety Population

Implementation Note: This will be similar to Figure 34. Groups include: 9-17 yrs, 10^9 TCID₅₀ Sing2016 M2SR, 1 Dose; 9-17 yrs, Placebo, 1 Dose

Figure 43: Participant-Level Incidence of Serious Adverse Events by MedDRA® System Organ Class and Maximum Severity – Participants 2-8 Years Old – Safety Population

Implementation Note: This will be similar to Figure 34. Groups include: 2-8 yrs, 10^8 TCID₅₀ Sing2016 M2SR, 1 Dose; 2-8 yrs, 10^9 TCID₅₀ Sing2016 M2SR, 1 Dose; 2-8 yrs, 10^9 TCID₅₀ Sing2016 M2SR, 2 Doses; 2-8 yrs, Placebo, 1 or 2 Doses

Figure 44: Participant-Level Incidence of Serious Adverse Events by MedDRA® System Organ Class and Maximum Severity – All Participants – Safety Population

Implementation Note: This will be similar to Figure 34. Groups include: Vaccine Recipients, Placebo Recipients

Figure 45: Participant-Level Incidence of New-Onset Chronic Medical Conditions by MedDRA® System Organ Class and Maximum Severity – Participants 9-17 Years Old – Safety Population

Implementation Note: This will be similar to Figure 34. Groups include: 9-17 yrs, 10^9 TCID₅₀ Sing2016 M2SR, 1 Dose; 9-17 yrs, Placebo, 1 Dose

Figure 46: Participant-Level Incidence of New-Onset Chronic Medical Conditions by MedDRA® System Organ Class and Maximum Severity, Participants 2-8 Years Old – Safety Population

[figure not shown]
Implementation Note: This will be similar to Figure 34. Groups include: 2-8 yrs, 10^8 TCID₅₀ Sing2016 M2SR, 1 Dose; 2-8 yrs, 10^9 TCID₅₀ Sing2016 M2SR, 1 Dose; 2-8 yrs, 10^9 TCID₅₀ Sing2016 M2SR, 2 Doses; 2-8 yrs, Placebo, 1 or 2 Doses

Figure 47: Participant-Level Incidence of New-Onset Chronic Medical Conditions by MedDRA® System Organ Class and Maximum Severity – All Participants – Safety Population

Implementation Note: This will be similar to Figure 34. Groups include: Vaccine Recipients, Placebo Recipients

Figure 48: Frequency of Non-Serious Unsolicited Adverse Events in the 28 Days Post Dosing by MedDRA® System Organ Class and Severity – Participants 9-17 Years Old – Safety Population

Implementation Note: Panels will be included for each analysis group (9-17 yrs, 10^9 TCID₅₀ Sing2016 M2SR, 1 Dose; 9-17 yrs, Placebo, 1 Dose)

Similar Figures:

Figure 49: Frequency of Non-Serious Unsolicited Adverse Events in the 28 Days Post Dose 1 by MedDRA® System Organ Class and Severity – Participants 2-8 Years Old – Safety Population

Implementation Note: This will be similar to Figure 48. Groups include: 2-8 yrs, 10^9 TCID₅₀ Sing2016 M2SR, 1 or 2 Doses; 2-8 yrs, 10^8 TCID₅₀ Sing2016 M2SR, 1 Dose; 2-8 yrs, Placebo, 1 or 2 Doses

Figure 50: Frequency of Non-Serious Unsolicited Adverse Events in the 28 Days Post Dose 2 by MedDRA® System Organ Class and Severity – Participants 2-8 Years Old – Safety Population

Implementation Note: This will be similar to Figure 48. Groups include: 2-8 yrs, 10^9 TCID₅₀ Sing2016 M2SR, 2 Doses; 2-8 yrs, Placebo, 2 Doses

Figure 51: Frequency of Non-Serious Unsolicited Adverse Events in the 28 Days Post Any Dose by MedDRA® System Organ Class and Severity – Participants 2-8 Years Old – Safety Population

Implementation Note This will be similar to Figure 48. Groups include: 2-8 yrs, 10^9 TCID₅₀ Sing2016 M2SR, 2 Doses; 2-8 yrs, Placebo, 2 Doses

Figure 52: Frequency of Non-Serious Unsolicited Adverse Events in the 28 Days Post Dose 1 by MedDRA® System Organ Class and Severity – All Participants – Safety Population

Implementation Note: This will be similar to Figure 48. Groups include: Vaccine Recipients, Placebo Recipients

Figure 53: Frequency of Adverse Events of Special Interest by MedDRA® System Organ Class and Severity – Participants 9-17 Years Old – Safety Population

Implementation Note: This will be similar to Figure 48. Groups include: 9-17 yrs, 10^9 TCID₅₀ Sing2016 M2SR, 1 Dose; 9-17 yrs, Placebo, 1 Dose

Figure 54: Frequency of Adverse Events of Special Interest by MedDRA® System Organ Class and Severity – Participants 2-8 Years Old – Safety Population

Implementation Note: This will be similar to Figure 48. Groups include: 2-8 yrs, 10^8 TCID₅₀ Sing2016 M2SR, 1 Dose; 2-8 yrs, 10^9 TCID₅₀ Sing2016 M2SR, 1 Dose; 2-8 yrs, 10^9 TCID₅₀ Sing2016 M2SR, 2 Doses; 2-8 yrs, Placebo, 1 or 2 Doses

Figure 55: Frequency of Adverse Events of Special Interest by MedDRA® System Organ Class and Severity – All Participants – Safety Population

Implementation Note: This will be similar to Figure 48. Groups include: Vaccine Recipients, Placebo Recipients

Figure 56: Frequency of Serious Adverse Events by MedDRA® System Organ Class and Severity – Participants 9-17 Years Old – Safety Population

Implementation Note: This will be similar to Figure 48. Groups include: 9-17 yrs, 10^9 TCID₅₀ Sing2016 M2SR, 1 Dose; 9-17 yrs, Placebo, 1 Dose

Figure 57: Frequency of Serious Adverse Events by MedDRA® System Organ Class and Severity – Participants 2-8 Years Old – Safety Population

Implementation Note: This will be similar to Figure 48. Groups include: 2-8 yrs, 10^8 TCID₅₀ Sing2016 M2SR, 1 Dose; 2-8 yrs, 10^9 TCID₅₀ Sing2016 M2SR, 1 Dose; 2-8 yrs, 10^9 TCID₅₀ Sing2016 M2SR, 2 Doses; 2-8 yrs, Placebo, 1 or 2 Doses

Figure 58: Frequency of Serious Adverse Events by MedDRA® System Organ Class and Severity – All Participants – Safety Population

Implementation Note: This will be similar to Figure 48. Groups include: Vaccine Recipients, Placebo Recipients

Figure 59: Frequency of New-Onset Chronic Medical Conditions by MedDRA® System Organ Class and Severity – Participants 9-17 Years Old – Safety Population

Implementation Note: This will be similar to Figure 48. Groups include: 9-17 yrs, 10^9 TCID₅₀ Sing2016 M2SR, 1 Dose; 9-17 yrs, Placebo, 1 Dose

Figure 60: Frequency of New-Onset Chronic Medical Conditions by MedDRA® System Organ Class and Severity, Participants 2-8 Years Old – Safety Population

Implementation Note: This will be similar to Figure 48. Groups include: 2-8 yrs, 10^8 TCID₅₀ Sing2016 M2SR, 1 Dose; 2-8 yrs, 10^9 TCID₅₀ Sing2016 M2SR, 1 Dose; 2-8 yrs, 10^9 TCID₅₀ Sing2016 M2SR, 2 Doses; 2-8 yrs, Placebo, 1 or 2 Doses

Figure 61: Frequency of New-Onset Chronic Medical Conditions by MedDRA® System Organ Class and Severity – All Participants – Safety Population

Implementation Note: This will be similar to Figure 48. Groups include: Vaccine Recipients, Placebo Recipients

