The first two groups to be vaccinated will be Cohorts 1 and 2. Cohort 1 consists of 45 children 9–17 years old. Thirty of them will receive one dose of the vaccine at a dose of 10^9 TCID₅₀, and 15 will receive one dose of placebo. Cohort 2 comprises 45 children 2–8 years old. Thirty of them will receive one dose of the vaccine at a dose of 10^8 TCID₅₀ and 15 will receive one dose of placebo. Sites will enroll participants into Cohorts 1 and 2 simultaneously. Once 25 or more participants in each of the first 2 cohorts (Cohorts 1 and 2) have completed Day 8, the SRC will evaluate if any halting rules are met and if it is deemed safe, enrollment in Cohort 3 may open. Enrollment within each cohort will not halt during the SRC review. Cohort 2 must fully enroll before enrollment in Cohort 3 may begin. If any halting rules are met or if the SRC raises any safety concerns other than halting rules that should be independently reviewed, the external Safety Monitoring Committee (SMC) will meet to discuss the data prior to progression to the next cohort.

Cohort 3 consists of 25 children 2–8 years old. Fifteen of them will receive one dose of vaccine at 10^9 TCID₅₀ and 10 will receive one dose of placebo. Once all 25 participants in Cohort 3 have completed Day 8 of follow-up, similar to Cohorts 1 and 2, the SRC will review to ensure no

halting rules are met and if no rules are met and the SRC determines it is safe to proceed, simultaneous enrollment into Cohorts 4 and 5 can begin. If any halting rules are met or any concerns are raised by the SRC, an external SMC may meet to discuss the data for recommendations on either progression or clinical trial modification before progression to the next cohort.

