Cohort 4 consists of 25 children 2-8 years old; 15 of them will receive two doses of vaccine at 10^9 TCID₅₀ and 10 will receive two doses of placebo, with a 28-day interval between the first and second doses. Cohort 5 will enroll 8 influenza naïve children (defined as children without receipt of influenza vaccine and without previous documented influenza infection) who are 6-23 months old who will be randomly assigned to receive two doses of 10^7 TCID₅₀ Sing2016 M2SR (n=6) or two doses of placebo (n=2) with a 28-day interval between the first and second dose. Once all 8 participants in Cohort 5 have completed Day 8 of follow-up after the first dose, the SRC will conduct a safety assessment before beginning enrollment in Cohort 6. Once 6 of the 8 participants in Cohort 5 have completed Day 4 after the second dose (e.g., Study Day 32), the following process will be implemented prior to receipt of the second dose for any participant in Cohort 6:

1. An email will be sent from the site to the SDMCC attesting that all data entry through Day 4 after the second dose (e.g., Study Day 32) for at least 6 participants in Cohort 5 has been completed.
2. The SDMCC will perform data cleaning as it pertains to assessment of the halting rules.
3. The SDMCC will assess if there were any halting rules met based on data entered in the data system and email DMID indicating what halting rules, if any, were met based on data entered in the data system.
 - a. If any of the halting rules were met, the study will halt and a review by the SMC, sponsor, and investigators will convene as specified in [Section 7.1](#).
 - b. If none of the halting rules were met, DMID will confirm that the study may proceed as per-protocol.

Cohorts 6 and 7 will also enroll 6 to 23-month-olds who are influenza-naïve. Cohort 6 will consist of 26 children. A lead-in group of 8 children will be randomly assigned to receive either two doses of 10^8 TCID₅₀ of the Sing2016 M2SR (n=6) or two doses of placebo (n=2). Once the first 8 children have completed Day 8 of follow up after the first dose, the SRC will review the safety and determine if Cohort 7 may open to enrollment. Cohort 7 enrollment will not begin until Cohort 6 is fully enrolled. Similar to other cohorts, the additional 18 children in Cohort 6 may continue to enroll during the SRC review.

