8.1.1.3. Unsolicited Adverse Events

When calculating the incidence of adverse events on the participant-level, each participant will only be counted once at the maximum value of the respective variable (e.g., maximum severity, maximum relatedness, etc.) and any repetitions of adverse events within a participant will be ignored. All adverse events reported will be included in the summaries and analyses.

The number and percentage of participants reporting at least one unsolicited adverse event will be summarized by MedDRA SOC and PT. Denominators for percentages are the number of participants who received the vaccination being summarized where applicable.

The following summaries of AEs will be provided:

- Incidence of the following by severity and relationship to study product
 - Non-serious unsolicited AEs in the 28 days following each study vaccination and across study vaccinations ([Table 40](#) through [Table 50](#))
 - AESIs ([Table 51](#) through [Table 58](#))
 - SAEs ([Table 59](#) through [Table 66](#))
 - NOCMCs ([Table 67](#) through [Table 74](#))
- Bar chart of the incidence of the following by severity of:
 - Non-serious unsolicited AEs in the 28 days following each study vaccination and across study vaccinations ([Figure 34](#) through [Figure 38](#))
 - AESIs ([Figure 39](#) through [Figure 41](#))
 - SAEs ([Figure 42](#) through [Figure 44](#))
 - NOCMCs ([Figure 45](#) through [Figure 47](#))
- Total frequency by severity, relationship to study product, and resolution of:
 - Non-serious unsolicited AEs in the 28 days following each study vaccination and across study vaccinations ([Table 75](#) through [Table 85](#))
 - AESIs ([Table 86](#) through [Table 93](#))
 - SAEs ([Table 94](#) through [Table 101](#))
 - NOCMCs ([Table 102](#) through [Table 109](#))

- Bar chart of frequency by severity of
 - Non-serious unsolicited AEs following each study vaccination and across study vaccinations ([Figure 48](#) through [Figure 52](#))
 - AESIs ([Figure 53](#) through [Figure 55](#))
 - SAEs ([Figure 56](#) through [Figure 58](#)),
 - NOCMCs ([Figure 59](#) through [Figure 61](#))

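### Total adverse-event frequency (SAP Tables 75-109, Figures 48-61) is planned as event counts with no per-participant rate, set side by side across groups of unequal size

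*SAP*

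**What the plan says.** SAP 4.6.1 names frequency, beside incidence and severity, as a dimension on which safety is assessed. SAP 8.1.1.3 then plans two kinds of output for unsolicited events.

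- **Incidence.** Each participant is counted once. Tables 40-74 follow the Table 40 shell, which has n, % and a 95% CI. Figures 34-47 chart participant-level incidence.
- **Frequency.** Tables 75-109 are introduced as "Total frequency by severity, relationship to study product, and resolution of" four event classes: non-serious unsolicited AEs, AESIs, SAEs and NOCMCs. The Table 75 shell has a total-events column and n columns for severity, relationship and resolution. It has no percentage or rate. Bar charts follow in Figures 48-61, with titles that begin "Frequency of Non-Serious Unsolicited Adverse Events in the 28 Days Post Dosing" (Figure 48), "Frequency of Adverse Events of Special Interest by" (Figures 53-55) and "Frequency of Serious Adverse Events by" (Figures 56-58).

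SAP 5.1 also treats frequencies and percentages as different quantities. The notes to Figures 48-61 name the groups to be shown, vaccine and placebo together, and mention no denominator or scaling.

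The Protocol synopsis (1.1) gives the planned sizes:

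- For Cohort 1: "Thirty of them will receive one dose of the vaccine at a dose of 10^9 TCID₅₀, and 15 will receive one dose of placebo"
- For Cohort 2: "Thirty of them will receive one dose of the vaccine at a dose of 10^8 TCID₅₀ and 15 will receive one dose of placebo"
- For Cohort 3: "Fifteen of them will receive one dose of vaccine at 10^9 TCID₅₀ and 10 will receive one dose of placebo"
- For Cohort 4: "15 of them will receive two doses of vaccine at 10^9 TCID₅₀ and 10 will receive two doses of placebo"

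SAP 8 pools the placebo recipients of Cohorts 2, 3 and 4.

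**The concern.** A bar that shows a count reflects the event rate multiplied by the group size. Where two panels have different N, equal rates give unequal bars. Here the imbalance does not run one way. In 9-17-year-olds and in the all-participant charts the vaccine group is the larger. In the AESI, SAE and NOCMC charts for 2-8-year-olds, each 10^9 TCID50 group is less than half the size of the pooled placebo group. A reader who moves through the series cannot apply one mental correction.

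Figures 48-61 are the only planned charts of total unsolicited events. The incidence charts count each child once, so they do not show repeat events. At stake is a fair visual reading of one stated safety variable, not the primary estimates.

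**Working it through.** **Inputs.** Planned vaccine/placebo sizes are 30/15 (Cohort 1), 30/15 (Cohort 2), 15/10 (Cohort 3) and 15/10 (Cohort 4), from Protocol 1.1 and SAP Table 2.

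- All vaccine, Cohorts 1-4: 30 + 30 + 15 + 15 = 90
- All placebo, Cohorts 1-4: 15 + 15 + 10 + 10 = 50
- Pooled placebo, 2-8 years: 15 + 10 + 10 = 35

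**Check against the plan's own figures.** SAP Table 3 uses N=90 for vaccine recipients in Cohorts 1-4, as above. Its probabilities of at least one event are reproduced by 1 − (1 − p)^N. At p = 1%, N=30 gives 26.0% (SAP: 26) and N=90 gives 59.5% (SAP: 59.5). The SAP states no bar ratio, so there is none to reproduce.

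**Ratio at equal rates.** Expected count = rate × N, so the expected vaccine:placebo ratio is N(vaccine)/N(placebo).

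| Figures | Comparison | Ratio |
|---|---|---|
| 48, 53, 56, 59 | 9-17 years, 30 v 15 | 2.00 |
| 52, 55, 58, 61 | all participants, 90 v 50 | 1.80 |
| 50, 51 | two-dose groups, 15 v 10 | 1.50 |
| 49 | 10^8 group, 30 v 35; 10^9 groups combined, 30 v 35 | 0.86 each |
| 54, 57, 60 | 10^8 group, 30 v 35 | 0.86 |
| 54, 57, 60 | each 10^9 group, 15 v 35 | 0.43 |

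In Figures 54, 57 and 60, a 10^9 group needs 35/15 = 2.33 times the placebo rate to give an equal expected count. At an illustrative 0.4 events per child in every group, expected counts are 12 v 6 in 9-17-year-olds and 6 v 14 for a 10^9 group against pooled placebo.

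**How often the larger group would show the larger count with no vaccine effect.** The documents give no event rates, so these are assumptions shown over a range. Counts are taken as independent Poisson.

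| Events per child | 30 v 15 | 90 v 50 | 35 v 15 |
|---|---|---|---|
| 0.5 | 93% | 99% | 97% |
| 0.1 | 68% | 83% | 75% |
| 0.02 | 36% | 56% | 41% |
| 0.01 | 23% | 43% | 26% |

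At low rates ties take over: for 30 v 15 at 0.01 events per child, the counts are equal 67% of the time. The charts are also split by system organ class and severity, so a single bar carries a lower rate than the total.

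**After the change.** With events per 100 participants, equal rates give an expected ratio of 1.00 in every figure.

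**The case against.** The strongest reply is that this is a supplementary display, and that the plan already supplies what a careful reader needs. Most of that stands.

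- The primary endpoints (SAP 3.2) are numbers and percentages of participants. Tables 40-74 and Figures 34-47 report those. A reader might infer that the primary safety analysis is distorted; the documents do not support that.
- A reader might infer that the count charts hide an excess of wheeze, SAEs or NOCMCs at 10^9. They do not, taken with the rest of the plan. Figures 40, 43 and 46 chart participant-level incidence for the same 2-8-year groups. Tables 110-112 list every AESI, SAE and NOCMC, and Table 113 details the wheezing events.
- The tables are not without a denominator. The titles of Tables 75-109 carry the Safety population N, and SAP 5.1 requires the population size on every table. Only a rate is absent.
- The Figure 48 mock-up is not reproduced. A count axis is a fair inference from the wording and the Table 75 shell. A common axis across panels is assumed, and whether the mock-up prints N cannot be known.
- Nine of the 14 figures (53-61) show AESIs, SAEs or NOCMCs. These may hold few or no events, and size imbalance then matters little.

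What the reply does not answer is that frequency is itself a stated safety variable. Incidence cannot stand in for it where events recur, and the series places unequal groups side by side with no normalisation stated.

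**Conclusion.** The point holds as a flaw in a supplementary display. Total event frequency is planned as counts with no per-participant rate. At equal rates the expected vaccine:placebo ratio runs from 2.0 down to 0.43 across the series. The extremes apply to seven of the 14 figures: 2.0 in four, and 0.43 in three for the 10^9 groups. Figure 49, at 0.86, is nearly balanced.

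This rests on the planned sizes, from which actual enrolment may depart slightly, on the inferred count axis, and on a shared scale across panels. It would be too strong to say that the charts will show a false vaccine excess. The ratios are expectations under equal rates, and the chance of a visibly longer bar falls quickly as events become rare.

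**What to change.** In Figures 48-61, plot events per 100 participants (events ÷ N × 100). Keep the raw count as a bar label and print N in each panel. Add an events-per-100 column to Tables 75-109; N is already in their titles.

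Define the denominator in SAP 8.1.1.3. For dose-specific displays it is the number who received that dose. For AESI, SAE and NOCMC displays it is the Safety population N of the group.

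The cost is SAP wording, revised shells and one derived column across 35 tables. No new data are needed, and no endpoint, population or trial procedure changes. The downside is that rates in groups of 10-15 are coarse: one event is 10 per 100 in a group of 10 and 6.7 per 100 in a group of 15. Keeping the count on the bar makes that visible. Where few or no events occur, the change will matter little.

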16.1.6 Listing of Participants Receiving Investigational Product

Listing 1: Listing of Participants Receipt of Study Product

[Implementation Note: sorted by cohort, then date of first vaccine administration, then participant ID]

Cohort	Study Product Assigned per Randomization	Study Product Received	Participant ID	Study Product Administration Deviations ^a	Date(s) of Study Product Administration
[e.g., Cohort 1, 2, 3, or 4]	[10 ⁸ TCID50 Sing2016 M2SR H3N2, 1 dose; 10 ⁹ TCID50 Sing2016 M2SR H3N2, 1 dose; 10 ⁹ TCID50 Sing2016 M2SR H3N2, 2 doses; Placebo]				[If one dose: DDMMMYYYY If two doses: DDMMMYYYY / DDMMMYYYY or DDMMMYYYY/ NA]

^a Includes administration of incorrect study product (including incorrect dosing) and study product administration out of window.

